To assess the comparative effectiveness of bicarbonate and saline and the benefit of NAC, we propose to conduct a multicenter, randomized, clinical trial designed and adequately powered to evaluate these interventions for the prevention of clinically important, adverse, patient-centered outcomes in high-risk Veterans undergoing cardiac and non-cardiac angiography. In this trial, 7,680 patients scheduled to undergo coronary or non-coronary angiography who are at increased risk of developing CIAKI and experiencing serious downstream outcomes (i.e., diabetics with eGFR <60 ml/min/1.73 m^2 or any patient with eGFR <45 ml/min/1.73 m^2) will be enrolled. Using a 2 x 2 factorial design, patients will be randomized to receive: 1) either IV isotonic sodium bicarbonate or IV isotonic saline and 2) either oral NAC or oral placebo prior to and following the angiographic procedure. We will assess the effectiveness of bicarbonate compared to saline and NAC compared to placebo for the prevention of a composite primary endpoint consisting of clinically significant, patient-centered events including death, need for acute dialysis, or persistent decline in kidney function, all within 90 days following the index angiogram. As a secondary outcome, we will assess differences in the development of CIAKI, defined by an increase in SCr of at least 0.5 mg/dL and/or 25% at 4 days following angiography. By enrolling a large population of high-risk Veterans and comparing the effectiveness of these interventions for the prevention of clinically relevant outcomes, the findings of this trial will definitively establish the role of bicarbonate and of NAC for the prevention of serious, adverse patient-centered events following angiography and will help inform the care delivered to a very large and growing population of patients undergoing angiographic procedures within the VA Healthcare System and the broader medical community.

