**Table 4 - Clinical trials comparing IV isotonic bicarbonate and IV isotonic saline to prevent CIAKI**

| Authors                             | Number of patients | Diabetes | Baseline SCr (mg/dL) | Definition of 1  outcome | Frequency of CIAKI bicarbonate | Frequency of CIAKI saline | Dialysis        | Death           | PDKF a | Assumed effect size of bicarbonate |
|-------------------------------------|--------------------|----------|----------------------|--------------------------------------|--------------------------------|---------------------------|-----------------|-----------------|-------------------|------------------------------------|
| Positive studies             |                    |          |                      |                                      |                                |                           |                 |                 |                   |                                    |
| Briguori et al.       | 219                | 52%      | 2.0                  | ↑ SCr ≥25%                           | 1.9%                           | 9.9%                      | 1%              | NA              | NA                | 86%                                |
| Masuda et al.         | 59                 | 31%      | 1.3                  | ↑ SCr ≥0.5mg/dL or ≥25%              | 6.6%                           | 34.5%                     | 7%              | 3%              | NA                | 85%                                |
| Merten et al.         | 119                | 48%      | 1.7-1.9              | ↑ SCr ≥25%                           | 1.7%                           | 13.6%                     | 0%              | NA              | NA                | 66%                                |
| Ozcan et al.          | 176                | 45%      | 1.4                  | ↑ SCr ≥0.5mg/dL or ≥25%              | 4.2%                           | 16.6%                     | 1%              | NA              | NA                | NR                                 |
| Pakfetrat et al.      | 192                | 30%      | 1.1                  | c                         | 4.2%                           | 12.5%                     | NA              | NA              | NA                | NR                                 |

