The need for dialysis as a component of our primary composite outcome refers to acute dialysis that may or may not lead to the chronic long-term requirement for renal replacement therapy. Given that we are proposing to enroll patients with Stage 3 and Stage 4 CKD (baseline eGFR 15-60 ml/min/1.73 m^2), it would be unexpected for these patients to progress to ESRD and need chronic dialysis within the 90-day follow-up period without an acute change in the trajectory of their chronic kidney disease. For patients who require acute dialysis in the setting of AKI, failure to recover kidney function within 90 days is the conventionally accepted transition from acute dialysis to end-stage renal disease and "chronic" dialysis. Thus, the need for dialysis within 90 days of contrast administration as a component of the primary outcome in this study is, by definition, acute dialysis. Patients who require acute dialysis following an episode of CIAKI may: i) experience a full or partial recovery of kidney function obviating the need for continued dialysis therapy; ii) develop ESRD necessitating chronic renal replacement therapy; or iii) die within 90 days before meeting the definition of ESRD/chronic dialysis. While CIAKI resulting in death or the need for chronic dialysis (i.e., ESRD) is relatively uncommon, the clinical significance of such outcomes is unequivocal. Less well recognized are the important adverse short and long-term implications of AKI that requires acute transient dialysis. Acute temporary dialysis, either with intermittent hemodialysis or continuous renal replacement therapy, is associated with important short-term adverse outcomes, including bleeding and blood-borne infection related to dialysis catheter placement, hemodynamic instability due to fluid and solute shifts during the dialysis procedure, and financial costs that may exceed \$500 to \$1,000 per treatment. Two recently published large studies demonstrated the longer-term implications of

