*d. Justification for 90-day time frame to assess the primary endpoint*

We chose to assess our primary endpoint at 90 days following angiography for two reasons. First, this represents a period of time during which adverse outcomes are more likely than not to be associated with the index angiographic procedure. Second, 90 days is commonly used in clinical practice and is proposed by the Kidney Disease: Improving Global Outcomes Foundation and the National Kidney Foundation to define the transition between acute and chronic impairment in kidney function. Therefore, persistent decline in kidney function measured at 90-days after the index angiographic procedure likely represents irreversible renal damage.

4. Secondary study outcomes

The secondary outcomes consist of:

- CIAKI defined by an increase in SCr of  $\geq 0.5$  mg/dL and/or  $\geq 25\%$  from the pre-procedure value at 4 days following angiography.
- Death within 90 days of the index angiographic procedure.

- The renal components of the primary endpoint:
  - Need for acute dialysis within 90 days of the index angiographic procedure
  - Persistent decline in kidney function at 90 days following the index angiographic procedure
- Hospitalization with acute coronary syndrome, heart failure, or cerebrovascular accident within 90 days following the index angiographic procedure. These outcomes will be defined as a primary or secondary discharge diagnosis of acute coronary syndrome (i.e., STEMI, NSTEMI, unstable angina), heart failure, or cerebrovascular accident documented in the VA electronic medical record or the hospital discharge summary obtained for non-VA hospitalizations. (This will include the occurrence of any of these events during the index hospitalization).
- All-cause re-hospitalization within 90 days of the index angiographic procedure assessed as episodes of re-hospitalization, days of hospitalization (inclusive of the index hospitalization), and hospital free days (alive and not in the hospital) through day 90.

Because AKI can occur following angiography for reasons unrelated to the administration of iodinated contrast, in a sensitivity analyses, we will also evaluate the development of CIAKI using the same threshold change in SCr, but excluding patients who experienced hypotension and/or who underwent cardiac surgery or non-cardiac vascular surgery within the 4 days following angiography.

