#### **E. Additional exploratory analyses**

We will explore several other hypotheses related to the binary 90 day MAKE-D outcome:

1. The combination of bicarbonate and NAC (interaction term) is more effective than bicarbonate or NAC alone.
2. (Per Protocol analysis) Bicarbonate, NAC, and their combination reduce the incidence of the primary outcome, MAKE-D, among subjects who received the full dose of bicarbonate.
3. (Per Protocol analysis) Bicarbonate, NAC, and their combination reduce the incidence of the primary outcome, MAKE-D, among subjects who received the full course of NAC.
4. Bicarbonate, NAC, and their combination reduce the incidence of the individual components of MAKE-D, each treated as a separate outcome: death, need for acute dialysis, and persistent decline in kidney function.
5. Bicarbonate, NAC, and their combination reduce the incidence of each of the individual cardiovascular components of the secondary outcome; namely acute coronary syndrome, heart failure, and cerebrovascular accident.
6. Bicarbonate, NAC, and their combination result in a greater reduction in the incidence of MAKE-D outcomes in subjects who develop CIAKI compared to those who do not develop CIAKI.
7. Bicarbonate, NAC, and their combination increase the mean number of days that participants are alive and hospitalization free (hospital free days) in the 90 days after angiography.

8. The benefits of bicarbonate, NAC, and their combination on MAKE-D outcomes are independent of the volume and rate of fluid administration above the minimum values prescribed in the protocol.

This brief list entails a large number of analyses. However, the sample size is large and the implicit hypotheses are highly inter-correlated. Thus, we anticipate that we can use a significance level of 1% ( $p = 0.01$ ) to detect associations of potential clinical importance in these exploratory analyses.

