#### Analyses of the association of CIAKI with MAKE-D events

Most previous studies of outcomes following procedures that utilized iodinated contrast have focused on acute increases in SCr within days of contrast administration (CIAKI). Compared to the events that comprise our 90-day primary outcome (MAKE-D), CIAKI occurs more frequently. While some episodes of CIAKI foreshadow MAKE-D events, some do not. Our analysis of data from the VA Austin databases demonstrated that compared to patients who do not develop CIAKI following angiography, patients who develop CIAKI have a nearly four-fold increased risk of experiencing a MAKE-D event. We propose to explore this relationship by stratifying the study participants into two groups: those who do and those who do not develop CIAKI. We will then run the logistic regression model for each stratum. This analysis may reveal different levels of effectiveness of the interventions based on whether CIAKI developed. We will carry out a more global analysis using log-linear models to address the same question by adding many interaction terms without explicit stratification. We chose a sensitive definition of CIAKI based on an increase in SCr of  $\geq 0.5$  mg/dL and/or  $\geq 25\%$ . This definition has been used in most prior trials and will permit us to compare our findings with prior studies on CIAKI. Nonetheless, we will also examine the incidence of CIAKI defined by more stringent criteria (AKIN definition), evaluate the effectiveness of our interventions on the prevention of larger changes in SCr, and assess the association of CIAKI defined by greater increases in SCr with MAKE-D outcomes.

Our protocol involves administering treatment before we assess the occurrence of CIAKI. Hence, the occurrence of CIAKI cannot be viewed as a simple treatment confounder. In fact, we

hypothesize that CIAKI lies on a causal pathway leading to MAKE-D events. Therefore, the exploratory analysis based on strata defined by the development of CIAKI is the first step in confirming the presence of such a causal pathway.

The above list is not exhaustive and the study team may choose to perform additional analyses on the PRESERVE cohort within the scope of the study population, diseases of interest, and data points collected.

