3.5.2. Secondary Endpoints

The secondary endpoints **except for CIAKI** for the study are assessed at 90 days post index procedure and they include the following individual outcomes:

(1) CIAKI defined by an increase in SCr of ≥ 0.5 mg/dL and/or $\geq 25\%$ increase at 96 hours following contrast administration, derived as follows.

$$(\text{SCr}_{96\text{Hours}} / \text{Scr pre-procedure}) * 100\% \geq 125\%$$

(2) Death from all causes to be verified by medical record and/or vital status registry documentation such as the VA Beneficiary Identification and Records Locator System, the National Center for Health Statistics National Death Index database, the Social Security Administration's Death master File.

(3) MAKE defined by (a) initiation of any modality of renal replacement therapy, which include intermittent hemodialysis, peritoneal dialysis, continuous renal replacement therapy, or prolonged intermittent renal replacement therapy, or (b) persistent decline in kidney function as defined in **3.5.1**.

(4) Hospitalization with acute coronary syndrome, heart failure, or cerebrovascular accident within 90 days following the index angiographic procedure. These outcomes will be defined as a primary or secondary discharge diagnosis of acute coronary syndrome (i.e., STEMI, NSTEMI, unstable angina), heart failure, or cerebrovascular accident documented in the VA electronic medical record or the hospital discharge summary obtained for non-VA hospitalizations. Note: This will include the occurrence of any of these events during the index hospitalization.

(5) All-cause re-hospitalization within 90 days of the index angiographic procedure assessed as episodes of re-hospitalization, days of hospitalization (inclusive of the index hospitalization), and hospital free days (alive and not in the hospital) through day 90.

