5.4. Secondary Analysis

For each of the five secondary endpoint events listed in **3.5.2** we will follow the same analytic strategy as the primary analysis described in **5.3**, where the odds of having an outcome will be estimated by modeling the outcome as a binary indicator of presence or absence of an event.

We will derive the Odds Ratios (i.e., the odds of the event of interest at 90 days post angioplasty among those allocated to IV isotonic sodium bicarbonate therapy compared to those allocated to IV isotonic saline, and among those allocated to NAC compared to those allocated to Placebo), and test for statistical significance of these odds ratios at $p=0.025$ level.

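### The SAP's derivation formula for CIAKI leaves out the 0.5 mg/dL limb of its own definition, so events can be missed when baseline SCr is above 2.0 mg/dL

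*SAP*

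**What the plan says.** **SAP 3.5.2(1).** The defining sentence has two limbs: an absolute rise in SCr of at least 0.5 mg/dL and a relative rise of at least 25%, either or both sufficing. It closes with "increase at 96 hours following contrast administration, derived as follows". One formula follows: SCr at 96 hours divided by pre-procedure SCr, as a percentage, is at least 125%. Item (1) ends there.

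**Protocol.** Both limbs appear wherever CIAKI is defined as an outcome. The Executive Summary has it "defined by an increase in SCr of at least 0.5 mg/dL and/or 25% at 4 days following angiography". Section VII.G.4 gives the same two thresholds, measured "from the pre-procedure value at 4 days following angiography". Sections II.B.2, V, XVII.C and XVII.E agree. XVII.E calls this a sensitive definition and gives the reason for choosing it: "This definition has been used in most prior trials and will permit us to compare our findings with prior studies on CIAKI".

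**Use of the variable.** Under SAP 5.4, for each secondary endpoint "the odds of having an outcome will be estimated by modeling the outcome as a binary indicator of presence or absence of an event", with the odds ratios tested at 0.025. Sections III.A.2.e and VIII.A.2 of the protocol single out CIAKI as a key secondary outcome.

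**The concern.** For a binary endpoint, the coded rule decides who is a case. Here one item of the SAP gives two rules that are not equivalent: a definition with two limbs and a derivation with one. A programmer who follows the formula builds a variable that is not the CIAKI the protocol defines. It is less sensitive, and it loses some of the comparability with earlier trials for which the definition was chosen.

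The patients affected are those with high baseline creatinine, and the trial sets out to include patients with markedly reduced kidney function: "Given that we are proposing to enroll patients with Stage 3 and Stage 4 CKD", with eGFR down to 15 (Protocol VII.G.3.b). If the text stays as it is, the choice between the two rules is left to whoever writes the program, possibly after outcome data are available.

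**Working it through.** **Inputs**
- Definition (SAP 3.5.2(1) sentence; Protocol VII.G.4): event if rise ≥ 0.5 mg/dL or rise ≥ 25% of baseline.
- Formula (SAP 3.5.2(1)): event if SCr 96 h / SCr pre-procedure ≥ 125%.
- The documents give no CIAKI count to reproduce, so the check compares the two rules directly.

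**Step 1: smallest rise that counts, at baseline SCr = b**
- Definition: min(0.5, 0.25 × b).
- Formula: 0.25 × b.
- The two are equal when 0.25 × b ≤ 0.5, that is, when b ≤ 2.0 mg/dL.

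**Step 2: size of the gap above 2.0 mg/dL**

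Excess rise = 0.25 × b / 0.5 − 1. Relative rises missed run from 0.5 / b up to, but not including, 25%.

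| Baseline SCr (mg/dL) | Rise needed, definition | Rise needed, formula | Excess | Ratio after a 0.5 mg/dL rise | Relative rises missed |
|---|---|---|---|---|---|
| 2.0 | 0.50 | 0.50 | 0% | 125.0% | none |
| 2.2 | 0.50 | 0.55 | 10% | 122.7% | 22.7% to <25% |
| 2.5 | 0.50 | 0.625 | 25% | 120.0% | 20.0% to <25% |
| 3.0 | 0.50 | 0.75 | 50% | 116.7% | 16.7% to <25% |
| 3.5 | 0.50 | 0.875 | 75% | 114.3% | 14.3% to <25% |
| 4.0 | 0.50 | 1.00 | 100% | 112.5% | 12.5% to <25% |

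**Step 3: worked case.** From 3.0 to 3.6 mg/dL the difference is 0.6, so the definition is met. The ratio is 3.6 / 3.0 = 120%, so the formula is not met.

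**Step 4: direction.** The ratio condition is one of the two limbs, so every event by the formula is also an event by the definition. The formula can drop events but cannot add any. A grid of baselines from 0.80 to 4.50 mg/dL and rises from 0 to 1.50 mg/dL, in steps of 0.01, confirms this: the first disagreement is at baseline 2.01, and no events are added.

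**Step 5: is the formula meant as the whole rule?** The nearest comparison is SAP 3.5.1(3), persistent decline in kidney function, which introduces its formula with the same words. There the ratio of at least 150% expresses the entire creatinine threshold (a rise of at least 50%), and the one further condition, the confirmatory sample, is written out in a sentence after the formula. In 3.5.2(1) nothing after the formula restores the 0.5 mg/dL limb.

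**The case against.** The strongest reply is that this is an incomplete formula and not a rival definition. The sentence that defines CIAKI has both limbs. The formula comes straight after the 25% limb and converts it to a ratio, whereas a 0.5 mg/dL difference needs no conversion. SAP section 1 lists the protocol among its sources, and the protocol repeats both limbs. A programmer would have to pass over all of this to code the ratio alone.

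Much of that stands. The documents show a drafting omission. They do not show that the endpoint was changed, or that the variable will be coded from the ratio alone. What does not stand is that the formula is merely illustrative. The text presents it as the derivation and does not limit it to one limb, and the parallel wording in SAP 3.5.1(3) introduces a formula that carries its full threshold.

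A reader might also infer that the error spreads to other analyses. Protocol XVII.E plans to compare intervention effects on the primary outcome "in subjects who develop CIAKI compared to those who do not develop CIAKI", and Protocol VII.G.4 and VIII.A.1 plan CIAKI sensitivity analyses at the same creatinine threshold. The documents do not support that inference. Those analyses are specified in the protocol, under its two-limb definition, and nothing ties them to the SAP formula. The five scenarios in SAP 5.3.5 concern the primary analysis, and none is on CIAKI.

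**Conclusion.** The point holds. The derivation in SAP 3.5.2(1) is wrong as written, because it gives the wrong case status to some patients who meet the definition in the same item. The documented consequence is confined to the CIAKI secondary endpoint tested in SAP 5.4.

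The size is exact for each patient and unknown for the trial. A case is lost only if baseline SCr exceeds 2.0 mg/dL and the rise is at least 0.5 mg/dL but under 25%. The conclusion assumes that the program follows the formula and that some enrolled patients have baselines above 2.0. The enrolled eGFR range makes the second likely, but the documents do not give the baseline SCr distribution. The bicarbonate trials in Protocol Table 4 report baselines of 1.0 to 2.0 mg/dL, but in other populations.

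Two stronger conclusions might be drawn, and neither is supported. One is that the omission favours one treatment: the rule is the same in all arms, so no directional bias is claimed. The other is a stated loss of power for CIAKI, which would need a fraction of cases lost that the documents do not supply. The primary endpoint uses a separate definition, and Protocol XVII.A.1 bases the sample size only on the two main effects for that endpoint, so neither is touched. The item should be corrected, but it does not threaten the main result.

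**What to change.** In SAP 3.5.2(1), replace the formula with:

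(SCr 96 h − SCr pre-procedure ≥ 0.5 mg/dL) OR (SCr 96 h / SCr pre-procedure ≥ 1.25)

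The smallest qualifying rise then becomes min(0.5, 0.25 × baseline), as the defining sentence and the protocol intend. Nothing changes at baselines of 2.0 mg/dL or below.

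The cost is one OR term in the SAP and in the analysis program. No new data are needed, because both creatinine values are already measured at the central laboratory (Protocol VII.A and VII.H.7). The protocol needs no amendment. The endpoint is not altered; the derivation is brought into line with it. The change is best made and dated before unblinded CIAKI data are analysed.

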3.5.3. Tertiary Endpoints

The tertiary endpoints for the study are assessed at one year post index procedure. The following endpoints will be obtained from study data and from registry documentation specified below.

1) Development of ESRD defined by the requirement for chronic dialysis for >3 months based on documentation in the United States Renal Data System database,

2) Death from all causes to be verified by medical record and/or vital status registry documentation such as the VA Beneficiary Identification and Records Locator System, the National Center for Health Statistics National Death Index database, the Social Security Administration's Death Master File.

